## 4 ANALYSIS SETS, TREATMENT GROUPS, AND SUBGROUPS

### 4.1 Analysis Sets

The following analysis sets are evaluated and used for presentation and analysis of the data:

- Enrolled: Subjects who sign an informed consent form and are assigned a subject identification number, i.e., nonmissing informed consent date. This analysis set is used mainly to assess study population and in by-subject listings.
- Full: Subjects in the enrolled analysis set who receive a randomized treatment assignment from the RTSM system, i.e., nonmissing RTSM randomization date. This analysis set is used mainly to assess study population.
- Safety: subjects in the enrolled analysis set who take  $\geq 1$  dose of study drug (DB rimegepant, OL rimegepant, or placebo), i.e., nonmissing study drug start date. This analysis set is used to assess study population and produce select by-subject listings.
  - DBT safety: subjects in the safety analysis set who take  $\geq 1$  dose of DB study drug (rimegepant or placebo), i.e., nonmissing DB study drug start date. This analysis set is used to assess study population, exposure, and on-DBT safety.
  - OL rimegepant safety: subjects in the safety analysis set who take  $\geq 1$  dose of OL rimegepant, i.e., nonmissing OL rimegepant start date. This analysis set is used to assess study population, exposure, and on-OL rimegepant safety.
    - Interim safety: subjects in the OL rimegepant safety analysis set with OL rimegepant start date – DB study drug last date  $> 7$  days. This analysis set is used to assess post-DBT pre-OL rimegepant safety.
  - DB or OL rimegepant safety: subjects in the safety analysis set who take  $\geq 1$  dose of DB or OL rimegepant, i.e., nonmissing DB or OL rimegepant start date. This analysis set is used to assess study population, exposure, and on-DB or OL rimegepant safety.
  - Follow-up safety: subjects in the safety analysis set whose last contact date is in the follow-up safety analysis period. This analysis set is used to assess follow-up safety.
- DBT efficacy: subjects in the full analysis set who are randomized only once and take  $\geq 1$  dose of DB study drug (rimegepant or placebo). This analysis set is used to analyze outcomes research during the DBT and OLE Phases.
  - Migraine: subjects in the DBT efficacy analysis set with  $\geq 14$  days of eDiary efficacy data (not necessarily consecutive) in both the OP and  $\geq 1$  month (4-week interval) in the DBT Phase (see Section 6.3.1). This analysis set is used to assess migraine days, acute migraine-specific medication days, acute migraine medication days, and headache days.
  - First month migraine: subjects in the DBT efficacy analysis set with  $\geq 24$  days of eDiary efficacy data (not necessarily consecutive) in both the OP and in first month (4-week interval) of the DBT Phase (see Section 6.3.3.3). This analysis set is used to assess efficacy endpoints per week.
  - First week EOD treated migraine: subjects in the DBT efficacy analysis set with (1)  $\geq 24$  days of eDiary efficacy data (not necessarily consecutive) in the OP, (2) 7 consecutive days of eDiary efficacy data in the first week of the DBT Phase, and (2) EOD dosing in the first week of the DBT Phase (see Section 6.3.3.5). This analysis set is used to assess efficacy endpoints per day in the first week of the DBT Phase.

See Section 7.1 for derived dates and Section 7.2 for analysis periods.

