### 3.2 Estimands

An estimand is the target of estimation to address the scientific question of interest posed by a study objective. The 4 attributes of an estimand include the population of interest, endpoint of interest, summary of the endpoint, and specification of how intercurrent events are reflected in the scientific question of interest.

For all objectives, the population of interest is defined through appropriate inclusion/exclusion criteria to reflect the targeted patient population for approval. Refer to the protocol for inclusion/exclusion criteria.

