Objective 3	Mean reduction from the OP in the number of migraine days per week and number of headache days per week by headache pain intensity (total; moderate or severe) in each week of the first 4 weeks of the DBT Phase
Efficacy Endpoint	Mean changes from the OP in the number of migraine days per week and number of headache days per week over time by week during the first 4 weeks of DBT, by headache pain intensity (total; moderate or severe)
Summary	Mean changes from the OP by treatment group using descriptive statistics and model, and difference in mean changes between treatment groups from model for the first month migraine analysis set
Intercurrent Events	Study drug discontinuation: hypothetical strategy Nonstudy prophylactic migraine medication use: treatment policy strategy Nonstudy acute migraine-specific medication use: composite strategy Use of nonstudy other medication to treat headache (migraine or nonmigraine) or aura: treatment policy strategy for migraine days; composite strategy for headache days
Objective 4	Proportions of subjects with <math>\geq 50\%</math> reduction from the OP in the number of migraine days per week and number of headache days per week by headache pain intensity (total; moderate or severe) in each week of the first 4 weeks of the DBT Phase
Efficacy Endpoint	Proportions of subjects with $\geq 50\%$ reduction from the OP in the number of migraine days per week and number of headache days per week over time by week during the first 4 weeks of DBT, by headache pain intensity (total; moderate or severe)
Summary	Percentages of subjects by treatment group, and difference in percentages between treatment groups using Mantel-Haenszel risk estimation for the first month migraine analysis set
Intercurrent Events	Study drug discontinuation: composite strategy Nonstudy prophylactic migraine medication use: treatment policy strategy Nonstudy acute migraine-specific medication use: composite strategy Use of nonstudy other medication to treat headache (migraine or nonmigraine) or aura: treatment policy strategy for migraine days; composite strategy for headache days

Objective 5	Proportions of subjects with a migraine day and headache day by headache pain intensity (total; moderate or severe) on each day of the first week of the DBT Phase

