## 5 SAMPLE SIZE, POWER, AND TYPE 1 ERROR

The study randomizes approximately 300 subjects per treatment group. Based on data from study C4951025 (BHV3000-305) and subgroup analysis from the galcanezumab Phase 3 program, we estimate that rimegepant provides roughly a 1.0-day advantage over placebo on the primary endpoint, and assuming a common standard deviation (SD) of 3.6 days. Assuming that roughly 280 subjects per treatment group contribute to the final migraine analysis dataset, the study has roughly 90% power on the primary endpoint at a 2-sided alpha level of 0.05.

In study C4951025 (BHV3000-305), rimegepant dosed EOD provided a 1.0-day advantage over placebo dosed EOD in subjects who were not taking prophylactic migraine medication through randomization. Using the data from study C4951025 (BHV3000-305), the SD of the primary endpoint was estimated to be roughly 3.6 days for these subjects.

Type 1 error is controlled using a 2-sided alpha level of 0.05 and hierarchical testing. First, the significance of the primary endpoint is evaluated at the 2-sided alpha level of 0.05 for rimegepant versus placebo. If the primary endpoint is not significant (i.e.,  $p\text{-value} > 0.05$ ), then any further tests on key secondary endpoints will have p-values presented only for descriptive purposes. If the primary endpoint is significant (i.e.,  $p\text{-value} \leq 0.05$ ), then the key secondary endpoints are tested hierarchically, each at a 2-sided alpha level of 0.05, in the order specified in Section 3.2.2.1. Thus, a key secondary endpoint is tested only if the preceding key secondary endpoint in the hierarchy is determined to be significant (i.e.,  $p\text{-value} \leq 0.05$ ). If a test in the hierarchy is not significant, then any further tests on endpoints in the sequence have p-values presented only for descriptive purposes, and no conclusions are drawn from those results.

For testing of other secondary or exploratory endpoints, no attempt is made to adjust for multiplicity. These endpoints are evaluated at an unadjusted, 2-sided alpha level of 0.05, and p-values are presented only for descriptive purposes.

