#### **6.3.3.4      *Percentages of Subjects With Reductions From OP in Numbers of Migraine Days per Week and Headache Days per Week Over Time in the First Month on DBT***

Analyses are based on the first month migraine analysis set with eDiary efficacy data dates in the OP and on-DBT efficacy analysis periods (see Section 7.2).

In analyses of migraine days per week, subjects must (1) achieve the reduction criterion from OP in the number of migraine days in the specified week, and (2) have  $\geq 1$  migraine day (absolute not prorated) of appropriate pain intensity in the OP analysis period to be classified as responders in the specified week. Otherwise, subjects are classified as failures in the specified week.

Headache day analyses by week are defined analogously to migraine day analyses by week.

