#### **6.3.3.5      *Percentages of Subjects with Migraine Days and Headache Days Over Time in the First Week on DBT***

Analyses are based on the first week EOD treated migraine analysis set, i.e., subjects in the DBT efficacy analysis set with (1)  $\geq 24$  days of eDiary efficacy data (not necessarily consecutive) in the OP analysis period, (2) 7 consecutive days of eDiary efficacy data in the first week (i.e., study days 1 through 7) of the on-DBT efficacy analysis period, and (3) EOD dosing in the first week of the on-DBT efficacy analysis period, defined as all 4 study days 1, 3, 5, and 7 being study drug dosing days and all 3 study days 2, 4, and 6 not being study drug dosing days (see Section 9.5).

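### Exploratory Objective 4 declares a composite strategy for stopping study drug, but its analysis set excludes anyone whose last dose is by Day 22, so discontinuation never makes a subject a failure

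*SAP*

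**What the plan says.** Objectives 3 and 4 (SAP 3.1, Exploratory Objectives) concern weekly migraine and headache days in each of the first four weeks of double-blind treatment. Both are analysed in the first month migraine set, which needs at least 24 "days of eDiary efficacy data (not necessarily consecutive) in both the OP and in first month (4-week interval) of the DBT Phase" (SAP 4.1). SAP 6.3.3.3 counts the Month 1 days within the on-DBT efficacy analysis period. SAP 7.2 ends that period at the last double-blind dose plus 1 day, or on the day before open-label treatment starts if that is earlier.

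For Objective 4, Table 4 of the SAP gives "Study drug discontinuation: composite strategy". SAP 3.2 explains how this works for binary endpoints: values after discontinuation plus 1 day are excluded, and subjects with missing data count as failures.

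The weekly responder rule (SAP 6.3.3.4) asks for the required reduction and at least one migraine day in the Observation Phase (OP). Then: "Otherwise, subjects are classified as failures in the specified week". It has no condition on discontinuation or on diary days in the week. The denominator at every week is the first month migraine set.

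For Objective 3, Table 4 gives a hypothetical strategy for discontinuation in the same set.

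**The concern.** A composite strategy is meant to let stopping treatment count against the treatment. That requires subjects who stop to stay in the denominator. Here the entry condition for the analysis set is measured after randomisation, over the whole of Month 1, and the diary count stops one day after the last dose. Staying on drug is not a written criterion of the set, but it follows from these two rules together. A subject who stops in Week 2 would then be absent even from the Week 1 comparison.

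Two things are at stake. The estimand declared for Objective 4 would not be the one estimated. And the weekly results would describe subjects who persisted into Week 4 with good diaries, not the randomised groups.

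**Working it through.** **The plan's own figure.** The only power statement concerns the primary endpoint: "the study has roughly 90% power on the primary endpoint at a 2-sided alpha level of 0.05", with "roughly a 1.0-day advantage over placebo on the primary endpoint, and assuming a common standard deviation (SD) of 3.6 days" and "roughly 280 subjects per treatment group contribute to the final migraine analysis dataset". The standard error is 3.6 × √(2/280) = 0.304. Then 1.0/0.304 = 3.287, and 3.287 − 1.960 = 1.327, which gives power of 90.8%. The figure reproduces. No sample size or power is given for Objectives 3 to 5, so the check below is one of counting.

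**Who can enter the set.** With the last dose on study day L, the on-DBT diary days in Month 1 number at most min(L + 1, 28). Entry needs 24.

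- L = 21: at most 22 days, excluded.
- L = 22: at most 23 days, excluded.
- L = 23: at most 24 days, can enter.

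A last dose on Day 22 or earlier therefore always removes the subject from all four weeks.

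**Can an analysed subject have a missing week?** At most 28 − 24 = 4 days can be missing. Even if all four fall in one week, that week has 7 − 4 = 3 diary days. SAP 6.3.3.3 sets no minimum per week, so the prorated weekly value always exists and the missing-as-failure rule is never triggered.

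**What happens to those who stop in Week 4 and stay in.** Week 4 is Days 22 to 28. A last dose on Day 23, 24, 25 or 26 leaves at most 3, 4, 5 or 6 diary days in Week 4. The value is prorated from those days and is not counted as a failure because of stopping.

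**Illustration of size (assumed rates).** The documents give neither early dropout nor weekly response rates. Assume Week 4 response of 45% on rimegepant and 35% on placebo among subjects in the set. The planned analysis then shows 10.0 points whatever the dropout. If early stoppers, with proportions dR and dP, stay in as failures, the difference is 0.45(1 − dR) − 0.35(1 − dP):

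- 5% and 5%: 0.4275 − 0.3325 = 9.5 points
- 6% and 2%: 0.423 − 0.343 = 8.0 points
- 10% and 5%: 0.405 − 0.3325 = 7.3 points
- 2% and 6%: 0.441 − 0.329 = 11.2 points

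This applies to Week 4, where anyone stopping by Day 22 has at most 2 diary days. In earlier weeks fewer subjects would have stopped, and those who stop later keep their observed weeks.

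**Diary rule alone.** If each day is completed independently with probability 80%, 90% or 95% (assumed), 31.5%, 85.8% or 98.8% of subjects reach 24 of 28 days. At each of these rates more than 99.9% reach the 14 of 28 used for monthly endpoints. Real diary completion is not independent from day to day, so these figures only show how much stricter the 24-day rule can be.

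**The case against.** The strongest reply is that little depends on these endpoints. They are exploratory, outside the testing hierarchy, and their p-values are descriptive (SAP 5). The controlled early endpoint, key secondary 2 (Weeks 1 to 4), uses the migraine set, which has no 24-day rule. Exploratory Objective 2 already gives a Month 1 responder rate in which fewer than 14 diary days is a failure and the denominator is the migraine set (SAP 6.3.2.1). All of this stands and limits the importance of the point. It does not make the declared strategy for Objective 4 operate. The Month 1 responder analysis also loses the very earliest stoppers: a last dose by Day 12 leaves at most 13 on-DBT diary days, so such a subject is outside the migraine set.

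A reader might infer more than the documents support in four respects.

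- **That Objective 3 breaks its declared strategy in the same way.** It declares a hypothetical strategy, so stoppers are not meant to be failures. The point there is only that observed early weeks are discarded.
- **That the Objective 5 set is an error.** That set requires all 7 diary days in Week 1 and exact dosing, with the four odd-numbered days "being study drug dosing days and all 3 study days 2, 4, and 6 not being study drug dosing days". It is named for this, and Table 4 lists discontinuation as not applicable. It is a disclosed adherence-restricted analysis.
- **That SAP 3.2 contradicts the restricted sets.** The sentence "For all objectives, the population of interest is defined through appropriate inclusion/exclusion criteria" defines the target population. SAP 3.2 refers to 4.1 for the analysis sets, and Table 4 names the set for each objective.
- **That early dropout can be read from the plan's counts.** The 480 of 600 is an estimate of entry to the open-label phase, and completers may decline or be ineligible. The 280 of 300 is the assumed size of the migraine set. Neither is a rate of stopping in Month 1.

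**Conclusion.** The point holds for Objective 4. By the SAP's own definitions, no subject in the first month migraine set can become a weekly failure through discontinuation, and everyone whose last dose is by Day 22 is absent from all four weeks. This is exact counting and rests on no assumption. For Objective 3 the consequence is smaller: observed weeks from excluded subjects are not used, although the repeated-measures model could take them.

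The size and direction of any bias cannot be stated. The 7.3 to 11.2 points against 10.0 depend on assumed response and dropout rates, and the bias changes sign with the arm that loses more subjects. The primary and key secondary conclusions are unaffected. This is a worthwhile correction, not a serious defect.

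**What to change.** In SAP 4.1 and 6.3.3.3 to 6.3.3.4, base Objectives 3 and 4 on DBT efficacy subjects with at least 24 OP diary days, with no Month 1 diary or persistence condition.

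- **Objective 4:** keep all of these subjects in the denominator at every week. Count a week as a failure if it has too few on-DBT diary days, whether from discontinuation or missed diaries. Fewer than 4 of 7 would match the proportion in the 14-of-28 monthly rule.
- **Objective 3:** include every evaluable week in the existing repeated-measures model.
- **Current first month set:** keep it as a labelled supplementary analysis.
- **Objective 5:** no change of set is needed. Describe the results as applying to subjects who dosed exactly on schedule with complete diaries. A by-day analysis in the wider set is optional.

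The cost is SAP wording and re-running existing programs; no new data are needed. Weekly values based on 4 to 6 diary days will be slightly noisier, and weekly response rates slightly lower.

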## 4.2 Treatment Groups

Treatment groups in the DBT Phase are rimegepant 75 mg EOD and placebo EOD. The safety analysis sets are assessed by as-treated treatment group (i.e., actual treatment received), the randomized, full, efficacy, and migraine analysis sets are assessed by as-randomized treatment group, and the enrolled analysis set is assessed overall.

If a subject takes  $\geq 1$  dose of planned randomized study drug, then that subject is considered to have as-treated treatment group equal to as-randomized treatment group (see Section 6.2.6.2).

If there are non-randomized subjects who take study drug, then the as-randomized treatment group of “not randomized” is included in the full analysis set augmented with the safety analysis set.

## 4.3 Subgroups

Subgroup tables present results by subgroup level and overall for subjects with nonmissing subgroup level data. Subgroup levels may be redefined or combined based on the availability of data.

The following efficacy subgroups are of interest for the migraine analysis set (see Section 6.2.5.1):

- Imputed randomization stratum 1 – number of migraine days in the 28-day OP:  $<8$ ,  $\geq 8$
- Imputed randomization stratum 2 – number of ROM medication categories with previous inadequate response:  $<3$ ,  $\geq 3$
- Imputed 4-level randomization stratum:
  - $<8$  migraine days in the 28-day OP and  $<3$  ROM medication categories with previous inadequate response
  - $<8$  migraine days in the 28-day OP and  $\geq 3$  ROM medication categories with previous inadequate response
  - $\geq 8$  migraine days in the 28-day OP and  $<3$  ROM medication categories with previous inadequate response
  - $\geq 8$  migraine days in the 28-day OP and  $\geq 3$  ROM medication categories with previous inadequate response.

Medical history of hypertension is a safety subgroup of interest for hypertension-related safety endpoints for the DBT and OL rimegepant safety analysis sets (see Section 6.2.5.3). Refer to the Core SAP for the subgroup definition.

## 5 SAMPLE SIZE, POWER, AND TYPE 1 ERROR

The study randomizes approximately 300 subjects per treatment group. Based on data from study C4951025 (BHV3000-305) and subgroup analysis from the galcanezumab Phase 3 program, we estimate that rimegepant provides roughly a 1.0-day advantage over placebo on the primary endpoint, and assuming a common standard deviation (SD) of 3.6 days. Assuming that roughly 280 subjects per treatment group contribute to the final migraine analysis dataset, the study has roughly 90% power on the primary endpoint at a 2-sided alpha level of 0.05.

In study C4951025 (BHV3000-305), rimegepant dosed EOD provided a 1.0-day advantage over placebo dosed EOD in subjects who were not taking prophylactic migraine medication through randomization. Using the data from study C4951025 (BHV3000-305), the SD of the primary endpoint was estimated to be roughly 3.6 days for these subjects.

Type 1 error is controlled using a 2-sided alpha level of 0.05 and hierarchical testing. First, the significance of the primary endpoint is evaluated at the 2-sided alpha level of 0.05 for rimegepant versus placebo. If the primary endpoint is not significant (i.e.,  $p\text{-value} > 0.05$ ), then any further tests on key secondary endpoints will have p-values presented only for descriptive purposes. If the primary endpoint is significant (i.e.,  $p\text{-value} \leq 0.05$ ), then the key secondary endpoints are tested hierarchically, each at a 2-sided alpha level of 0.05, in the order specified in Section 3.2.2.1. Thus, a key secondary endpoint is tested only if the preceding key secondary endpoint in the hierarchy is determined to be significant (i.e.,  $p\text{-value} \leq 0.05$ ). If a test in the hierarchy is not significant, then any further tests on endpoints in the sequence have p-values presented only for descriptive purposes, and no conclusions are drawn from those results.

For testing of other secondary or exploratory endpoints, no attempt is made to adjust for multiplicity. These endpoints are evaluated at an unadjusted, 2-sided alpha level of 0.05, and p-values are presented only for descriptive purposes.

## 6 STATISTICAL ANALYSES

All statistical analyses are performed using SAS statistical software (Version 9.4 or higher).

### 6.1 General

#### 6.1.1 Programmed Output

A list of TLFs and corresponding templates are presented separately in a mock TLF document corresponding to this SAP.

Refer to the Core SAP for additional details about programmed output.

Country is based on a site/country external file provided by the data management vendor.

### 6.1.1.1 Tables

#### Treatment Group Presentation

Treatment group presentation in tables by analysis set is shown in [Table 5](#). Exceptions are specified in subsequent sections as needed.

**Table 5 Treatment Group Presentation in Tables by Analysis Set**

Analysis Set	Number of Columns	Abbreviated Treatment Group
Enrolled	1	Overall
Full, DBT efficacy, migraine, safety, DBT safety, interim safety by treatment group and {overall}	2 to 3	Rimegepant 75 mg Placebo {Overall}
OL rimegepant safety, DB or OL rimegepant safety by treatment group/OL rimegepant and overall	3	DB RMG/OL RMG DB PBO/OL RMG Overall
Follow-up safety by treatment group/OL rimegepant status and overall	5	DB RMG/OL RMG DB PBO DB PBO to OL RMG DB PBO No OL RMG Overall

Results for study population also include overall treatment group (see [Section 6.2](#)).

Subgroup tables of efficacy endpoints have the same format as the main efficacy tables, but display each subgroup level in a separate row, and page break by subgroup level. A separate table is produced for each efficacy subgroup of interest.

